### 9.2. General Statistical Considerations

Statistical analysis of this study will be the responsibility of Lilly.

Continuous data will be summarized in terms of the mean, standard deviation, minimum, maximum, median, and number of observations. Categorical data will be summarized as frequency counts and percentages.

Any change to the data analysis methods described in the protocol will require an amendment ONLY if it changes a principal feature of the protocol. Any other change to the data analysis methods described in the protocol, and the justification for making the change, will be described

in the clinical study report (CSR). Additional exploratory analyses of the data will be conducted as deemed appropriate.

Complete details of the planned analyses will be documented in the SAP.

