When the MMRM is used, the model will include treatment, geographic region, screening MRI/CRP status, baseline value, visit, baseline value-by-visit, and treatment-by-visit interaction as fixed factors. The covariance structure to model the within-patient errors will be unstructured. If the unstructured covariance matrix results in a lack of convergence, the similar approach specified above for categorical MMRM will be used. The Kenward-Roger method will be used to estimate the denominator degrees of freedom. Type III tests for the least-squares (LS) means will be used for the statistical comparison; the 95% CI will also be reported. Treatment group comparisons with placebo at Week 16 (Visit 8), Week 52 (Visit 15), and all other visits will be tested.

When the ANCOVA is used, the model will include treatment, geographic region, screening MRI/CRP status and baseline value. Type III sums of squares for the LS means will be used for the statistical comparison; the 95% CI will also be reported.

The impact of ixekizumab starting dose of 160 mg versus 80 mg on time to onset (focusing on Week 4) and treatment response during Blinded Treatment Dosing Period will be summarized and evaluated. Details will be specified in the SAP.

For variables that are not collected at each postbaseline visit, data may exist at visits where the variable was not scheduled to be collected due to early discontinuation visits. In these situations,

data from the early discontinuation visit that does not correspond to the planned collection schedule will be excluded from the MMRM and Categorical MMRM analyses. However, the data will still be used in other analyses, including shift analyses, change from baseline to last-observation carried forward (LOCF) or modified baseline observation carried forward (mBOCF) endpoint analyses, and other categorical analyses.

Fisher's exact test will be used for all AE, baseline, discontinuation, and other categorical safety data. Continuous vital sign and laboratory values will be analyzed by an ANCOVA with treatment and baseline value in the model.

Patients who discontinue study treatment after Week 16 will continue to be followed for the scheduled visits for safety and efficacy assessment. The data collected post discontinuation of study treatment will be summarized separately.

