The primary analyses for continuous efficacy and health outcomes variables will be made using MMRM. The primary analyses for MRI endpoints will be made using analysis of covariance (ANCOVA). A secondary analysis for continuous efficacy and health outcomes variables will be made using ANCOVA.

When the MMRM is used, the model will include treatment, geographic region, screening MRI/CRP status, baseline value, visit, baseline value-by-visit, and treatment-by-visit interaction as fixed factors (except for the analysis of CRP, see paragraph below). The covariance structure to model the within-patient errors will be unstructured. The REML will be used. The Kenward-Roger method will be used to estimate the denominator degrees of freedom. Type III tests for the least-squares (LS) means will be used for the statistical comparison; the 95% CI will also be reported. Treatment group comparisons with placebo at Week 16 (Visit 8), Week 52 (Visit 15) and all other visits will be reported. If the unstructured covariance matrix results in a lack of convergence, the similar approach specified above for categorical MMRM will be used.

For the analysis of mean change from baseline and ratio of postbaseline to baseline in CRP, MMRM model will include treatment, geographic region, screening MRI/CRP status, visit, and treatment-by-visit interaction as fixed factors. Note for the ratio of postbaseline to baseline in CRP, analysis will be performed on the natural log transformed ratio.

When the ANCOVA is used, the model will include treatment, geographic region, screening MRI/CRP status, and baseline value (except for the analysis of CRP, see paragraph below).

Type III sums of squares for the Least Squares (LS) means will be used for the statistical comparison; the 95% CI will also be reported.

For the analysis of mean change from baseline and ratio of postbaseline to baseline in CRP, ANCOVA model will include treatment, geographic region and screening MRI/CRP status. Note for the ratio of postbaseline to baseline in CRP, analysis will be performed on the natural log transformed ratio.

For the analysis of ASDAS disease activity states (ie, inactive, low, high, and very high disease states), the repeated measures proportional odds model will include treatment, geographic region, screening MRI/CRP status, visit, and treatment-by-visit interaction.

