The impact of ixekizumab starting dose of 160 mg versus 80 mg on treatment response at Week 16 will be summarized and evaluated. Response rates in selected categorical variables (ASAS40/20, ASDAS<2.1, BASDAI50, ASDAS clinical important improvement, ASDAS major improvement) and LS mean change in selected continuous efficacy and health outcome measures (CRP, BASFI, BASDAI, spinal pain and SF-36 PCS) at Weeks 16 and 52 will be presented for patients randomized to ixekizumab Q2W or Q4W treatment regimen with ixekizumab 160 mg starting dose and with ixekizumab 80 mg starting dose.

For response rates, starting dose comparisons within ixekizumab Q2W or Q4W treatment regimens will be based on logistic regression model with treatment, starting dose, and treatment-by-starting-dose interaction (only ixekizumab Q2W and Q4W will be included in the analyses). Starting dose comparison combining ixekizumab Q2W and Q4W treatment regimens will be based on logistic regression model with only starting dose in the model.

For mean change analysis, starting dose comparisons within ixekizumab Q2W or Q4W treatment regimens will be based on MMRM model with treatment, starting dose, baseline value, visit, baseline value-by-visit, treatment-by-visit, treatment-by-starting dose, starting dose-by-visit, and treatment-by-starting dose-by-visit interactions as fixed factors. Starting dose comparison combining ixekizumab Q2W and Q4W treatment regimens will be based on MMRM model with starting dose, baseline value, visit, baseline value-by-visit, and starting dose-by-visit interaction as fixed factors. The differences in response rates and LS mean changes between starting doses and the corresponding 95% CI will be reported as well.

For variables that are not collected at each postbaseline visit, data may exist at visits where the variable was not scheduled to be collected, due to early discontinuation visits. In these situations, data from the early discontinuation visit that do not correspond to the planned collection schedule will be excluded from the MMRM and categorical MMRM analyses (Andersen and Millen 2013). However, the data will still be used in other analyses, including shift analyses, change from baseline to modified baseline observation carried forward (mBOCF) endpoint analyses, and other categorical analyses.

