**Table RHBX.6.3. Geographic Regions for Statistical Analysis**

Geographic Region	Countries
Europe	Austria, Russia a , Czech Republic, Finland, Poland, Germany, Romania, The Netherlands
non-Europe	United States, Canada, Argentina, Brazil, Mexico, Japan, Korea

a Russia is combined with European countries due to the preponderance of investigative sites in the western part of Russia.

In general, when an MMRM is to be used for analyses, baseline value and baseline-by-visit interactions will be included as covariates; when an ANCOVA is to be used for analyses, baseline value will be included as a covariate.

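### The SAP leaves measured baseline CRP out of both models that compare CRP with placebo, departs from the protocol in doing so, gives no reason, and loses precision in other-secondary analyses

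*SAP*

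**What the plan says.** Protocol 9.2.1 sets one MMRM and one ANCOVA for all continuous efficacy variables. For the MMRM: "When the MMRM is used, the model will include treatment, geographic region, screening MRI/CRP status, baseline value, visit, baseline value-by-visit" and the treatment-by-visit interaction. For the ANCOVA: "When the ANCOVA is used, the model will include treatment, geographic region, screening MRI/CRP status and baseline value". CRP is not excepted from either.

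SAP 6.1.2.1 repeats these models but attaches a qualifier to each: "except for the analysis of CRP, see paragraph below". The paragraphs that follow give the CRP versions, for change from baseline and for the log-transformed ratio of postbaseline to baseline. In the MMRM, "in CRP, MMRM model will include treatment, geographic region, screening MRI/CRP status, visit, and treatment-by-visit interaction as fixed factors". For the other, the "ANCOVA model will include treatment, geographic region and screening MRI/CRP status". Neither contains baseline CRP.

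SAP 6.2 states the default: "In general, when an MMRM is to be used for analyses, baseline value and baseline-by-visit interactions will be included as covariates", with a matching statement for ANCOVA. Neither 6.1.2.1, nor 6.2, nor the revision history says why CRP is treated differently.

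SAP Table RHBX.6.5 applies both CRP models to each ixekizumab regimen against placebo at every postbaseline visit, as other-secondary analyses.

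**The concern.** The screening MRI/CRP status that remains in the models is a three-level factor. Its CRP content is a dichotomy at 5 mg/L measured at Visit 1, up to 42 days before randomisation. The baseline itself is normally the Visit 2 measurement. Two patients with very different baseline CRP can fall in the same stratum, so the factor is a weak substitute for the measured value.

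Analysing a change or a log ratio without the baseline covariate fixes the slope of follow-up on baseline at 1. If the true slope differs, residual variance is larger than it need be, and chance imbalance in baseline CRP within a stratum goes uncorrected.

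At stake is the width of every CRP interval against placebo. CRP is an objective inflammation measure and a named other-secondary endpoint, but it lies outside the multiplicity scheme (SAP 6.10.4).

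**Working it through.** **1. Which SAP models keep baseline**

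| Analysis | Screening MRI/CRP status | Baseline value |
|---|---|---|
| Protocol 9.2.1, MMRM and ANCOVA | yes | yes |
| SAP 6.10.2, ASDAS change (MMRM) | yes | yes, with visit interaction |
| SAP 6.10.2, SIJ SPARCC score (ANCOVA) | yes | yes |
| SAP 6.1.2.1, starting dose, including CRP (MMRM) | no | yes, with visit interaction |
| SAP 6.1.2.1, CRP v placebo (MMRM and ANCOVA) | yes | **no** |

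Overlap with the stratum is therefore not a reason the SAP applies elsewhere. The SPARCC model adjusts for both the MRI-based stratum and the baseline MRI score. The ASDAS model adjusts for both the stratum and a baseline score that contains 0.579 × Ln(CRP+1). The pooled starting-dose model, an "MMRM model with starting dose, baseline value, visit, baseline value-by-visit, and starting dose-by-visit interaction as fixed factors", covers CRP but has no stratum factor and no placebo arm, so it is a looser parallel.

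**2. Would adjusting lose patients?** No. Change and ratio both need a baseline value, and SAP Table RHBX.6.4 substitutes Visit 1 CRP if Visit 2 is missing. Log baseline exists whenever the log ratio does.

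**3. Precision at a single visit (ANCOVA).** The plan states no CRP precision figure to reproduce, and no SD or correlation. Assume, within stratum, baseline SD 1, follow-up SD k and correlation r. The slope of follow-up on baseline is then kr.

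- Residual variance without baseline: 1 + k² − 2kr
- Residual variance with baseline: k²(1 − r²)
- Difference: (1 − kr)², which is zero only when the slope is 1
- SE ratio: √[(1 + k² − 2kr) / (k²(1 − r²))]

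At k = 1 the SE ratio reduces to √[2/(1 + r)], and the equivalent number of patients per 100 is 100(1 + r)/2:

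| r | SE ratio | Equivalent patients per 100 |
|---|---|---|
| 0.3 | √(2/1.3) = 1.240 | 65 |
| 0.5 | √(2/1.5) = 1.155 | 75 |
| 0.7 | √(2/1.7) = 1.085 | 85 |
| 0.9 | √(2/1.9) = 1.026 | 95 |

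A simulation of 4,000 trials (100 v 100, three strata plus region) gave model SE ratios of 1.24, 1.15, 1.08 and 1.02. With no true effect, the mean estimate was within 0.003 of zero in both models, so there is no bias.

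Varying k over r = 0.3 to 0.9:

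- k = 0.7: 43–57% larger. At r = 0.7, √(0.51/0.2499) = 1.429.
- k = 0.8: 25–41% larger. At r = 0.8, √(0.36/0.2304) = 1.25.
- k = 1.25: 0–13% larger. At r = 0.8 the slope is 1.25 × 0.8 = 1 and the loss is zero.

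The same formula applies to raw CRP change, with k the SD ratio on the raw scale.

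**4. Precision in the MMRM.** This used generalised least squares with known covariance, three arms of 100, and the 13 postbaseline CRP visits in the Schedule of Activities (Weeks 1 to 52). Two follow-up correlation structures were tried, with k = 1 and dropout at random. Excess SE of the log ratio without baseline and baseline-by-visit:

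| Time and assumed retention | r = 0.3 | 0.5 | 0.7 | 0.9 |
|---|---|---|---|---|
| Week 16, complete | 24% | 15% | 8% | 2–3% |
| Week 52, complete | 24% | 15% | 8% | 2–3% |
| Week 52, 60% placebo / 75% ixekizumab | 18–19% | 11–12% | 6–7% | 2% |
| Week 52, 35% placebo / 55% ixekizumab | 12–14% | 8–9% | 5% | 1% |

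**5. A second parameterisation.** Here the correlation is defined before conditioning on the stratum, and the screening CRP dichotomy is in both models. Assumptions: screening-to-baseline correlation 0.6–0.8 and 50–80% of patients with elevated CRP. With equal SDs the variance ratio is 1.40–1.55 at correlation 0.2, 1.20–1.28 at 0.5 and 1.07–1.09 at 0.8, so the SE is about 3–25% larger. With an SD ratio of 0.8 the variance ratio is 1.34–1.94. For raw change under a lognormal model it is 1.21–1.66, an SE 10–29% larger (√1.21 = 1.10, √1.66 = 1.29). Every scenario showed a loss.

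**The case against.** The strongest reply is that this is a declared choice and not a breach. The SAP flags the exception in both model statements and writes out the replacement models, so nothing is left to post hoc selection. Protocol 9.2 requires an amendment only for changes to principal features. For the rest it says: "Any other change to the data analysis methods described in the protocol, and the justification for making the change, will be described". The place it names for this is the clinical study report. That report is not to hand, and the SAP appendices are redacted, so the absence of a reason can be asserted only for the readable text. All of this stands. The departure is permitted, but a justification is still owed and none is visible.

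The size is also open to challenge. No CRP SD, correlation or retention rate is given, and the losses of 43–57% require follow-up SD to be well below baseline SD. The second parameterisation gives smaller figures, partly because its correlations are not within stratum. All scenarios use one r and one k for every arm, although an anti-inflammatory drug could change both in the active arms only. These points stand as limits on the numbers. They leave the direction unchanged: under the common-slope calculation the loss is zero only when the slope is 1.

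Finally, the SAP's safety laboratory ANCOVA keeps baseline, but it is not clear that it covers CRP. The argument here does not rely on it.

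**Conclusion.** The point holds. Both CRP models against placebo omit measured baseline CRP, the protocol's models include it, and no reason is visible. The effect is loss of precision, with no bias and no loss of patients. On the log-ratio scale with equal SDs, the SE is larger by roughly 3% to 25% for correlations from high to low, and by less at Week 52 if many patients have stopped contributing. The loss is larger if CRP variability falls after baseline, and it can vanish if variability rises so that the slope is near 1. All sizes rest on assumed correlations, SD ratios and retention.

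The consequence is confined to other-secondary analyses. The primary tests, the major secondary tests and ASDAS change are unaffected. The correction is worth making because it costs almost nothing.

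**What to change.** In SAP 6.1.2.1, change four model statements:

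- Log ratio: add baseline log CRP to the ANCOVA, and baseline log CRP with its visit interaction to the MMRM.
- Change: add baseline CRP to the ANCOVA, and baseline CRP with its visit interaction to the MMRM.
- Keep screening MRI/CRP status in all four.

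If the exception is retained, state the reason in the SAP and carry it into the clinical study report.

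One separate editorial item: SAP 6.10.4 refers to an earlier time point for the starting-dose comparison as described in 6.1.2, but 6.1.2 gives only Weeks 16 and 52. Name Week 4 there, as protocol 9.2.1 does.

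The cost is four model statements and one cross-reference. Baseline CRP is already available for every patient analysed.

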| 
 
• To explore the effect of starting dose (160 mg compared to 80 mg)
 
• To evaluate the incidence of anti-ixekizumab antibodies and its relationship to efficacy of ixekizumab
 
 
• To measure ixekizumab exposure and assess the relationship between exposure and efficacy and exposure and immunogenicity
 
 | 
 
• Onset of action and treatment response (ASAS, ASDAS, CRP, BASFI)
 
• Efficacy response rates listed below at Weeks 16 and 52 by treatment-emergent anti-drug antibody (TE-ADA) status and by neutralizing anti-drug antibody (NAb) status                             
 
○ Proportion of patients achieving ASAS40
 
○ Proportion of patients achieving ASAS20
 
○ Proportion of patients achieving ASDAS inactive disease
 
 
 
• Serum trough concentrations of ixekizumab
 
• Model parameters for the exposure-response relationship between ixekizumab serum trough concentrations and efficacy endpoints (for example, ASAS20, ASAS40) at Week 16 and/or Week 52
 
• Ixekizumab serum trough concentrations associated with anti-drug antibody (ADA) titer
 
  |
| 
Exploratory Objective
   |   |

| Objectives   | Endpoints  |
|--|------------|
| 

• CCI [REDACTED]

 | [REDACTED] |

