
 
• To explore the effect of starting dose (160 mg compared to 80 mg)
 
	
 
• Onset of action and treatment response (ASAS, ASDAS, CRP, BASFI, BASDAI, spinal pain and SF-36 PCS)
 

 
• To evaluate the incidence of anti-ixekizumab antibodies and its relationship to efficacy of ixekizumab
 
	
 
• Efficacy response rates listed below at Weeks 16 and 52 by treatment-emergent anti-drug antibody (TE-ADA) status and by neutralizing anti-drug antibody (NAb) status                         
 
○ Proportion of patients achieving ASAS40
 
 
 

[figure not shown]
Objectives	Endpoints
	
 
○ Proportion of patients achieving ASAS20
 
○ Proportion of patients achieving ASDAS <2.1
 

 
• To measure ixekizumab exposure and assess the relationship between exposure and efficacy and exposure and immunogenicity
 
	
 
• Serum trough concentrations of ixekizumab
 
• Model parameters for the exposure-response relationship between ixekizumab serum trough concentrations and efficacy endpoints (for example, ASAS20, ASAS40) at Week 16 and/or Week 52
 
• Ixekizumab serum trough concentrations associated with anti-drug antibody (ADA) titer
 

Exploratory Objective	

 
• CCI [REDACTED]
 
	
 
• CCI [REDACTED]
 

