## 5. Study Design

### 5.1. Summary of Study Design

Study I1F-MC-RHBX (RHBX) is a Phase 3, multicenter, randomized, double-blind, placebo-controlled, parallel-group, outpatient study examining the efficacy and safety of 2 ixekizumab treatment regimens (80 mg every 2 weeks [Q2W] and 80 mg every 4 weeks [Q4W] subcutaneous [SC]) as compared to placebo SC in patients with active nonradiographic axial spondyloarthritis (nonrad-axSpA) who are biological disease-modifying antirheumatic drug (bDMARD) naive, during a double-blind, 52-week treatment period (Period 2).

[Figure RHBX.5.1](#) illustrates the study design. Within the active treatment groups, half the patients will be given a 160-mg starting dose and the other half will be given an 80-mg starting dose.

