		Categorical MMRM (for ASDAS <2.1 only)	ITT Population	IXE80Q2W & IXE80Q4W vs. placebo at Weeks 16 and 52 and all other postbaseline visits in Period 2	Other secondary efficacy analyses (Section 6.10.4).
		Fisher’s exact test with NRI	ITT Population	IXE80Q2W & IXE80Q4W vs. placebo at Weeks 16 and 52 and all other postbaseline visits in Period 2	Other secondary efficacy analyses (Section 6.10.4).
		Logistic regression analysis with NRI (for ASDAS <2.1 only)	ITT Population	IXE80Q2W & IXE80Q4W Starting Dose 160 mg and 80 mg during Period 2	Other secondary efficacy analyses (Section 6.10.4).
		Subgroup analyses (for ASDAS <2.1 only)	ITT Population	IXE80Q2W & IXE80Q4W vs. placebo at Weeks 16 and 52	Subgroup analysis (Section 6.15.1)
		Descriptive statistics of ASDAS <2.1	IR Population	Period 2 post initiation of biologic rescue of ixekizumab 80 mg Q2W	Exploratory analyses (Section 6.10.6.1)
ASDAS	ASDAS Disease Activity States	Repeated measures proportional odds model analysis with NRI	ITT Population	IXE80Q2W & IXE80Q4W vs. placebo at all other postbaseline visits in Period 2	Other secondary efficacy analyses for primary outcome (Section 6.10.4)

Measure	Variable	Analysis Method (Sections 6.1 and 6.3)	Population (Section 6.1.1)	Comparison/Time Point	Analysis Type
ASDAS	ASDAS clinical important improvement; major improvement	Logistic regression analysis with NRI; Fisher's exact test with NRI	ITT Population	IXE80Q2W & IXE80Q4W vs. placebo at Weeks 16 and 52 and all other postbaseline visits in Period 2	Other secondary efficacy analyses (Section 6.10.4).
		Logistic regression analysis with NRI	ITT Population	IXE80Q2W & IXE80Q4W Starting Dose 160 mg and 80 mg during Period 2	Other secondary efficacy analyses (Section 6.10.4).
		Descriptive statistics of response rate	IR Population	Period 2 post initiation of biologic rescue of ixekizumab 80 mg Q2W	Exploratory analyses (Section 6.10.6.1)
BASDAI	BASDAI50	Logistic regression analysis with NRI	ITT Population	IXE80Q2W & IXE80Q4W vs. placebo at Weeks 16 and 52 and all other postbaseline visits in Period 2	Other secondary efficacy analyses (Section 6.10.4).
		Fisher's exact test with NRI	ITT Population	IXE80Q2W & IXE80Q4W vs. placebo at Weeks 16 and 52 and all other postbaseline visits in Period 2	Other secondary efficacy analyses (Section 6.10.4).
		Descriptive statistics of BASDAI50 response rate	IR Population	Period 2 post initiation of biologic rescue of ixekizumab 80 mg Q2W	Exploratory analyses (Section 6.10.6.1)

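### The starting-dose comparison on ASDAS uses three cut-offs only; ASDAS change from baseline should join the MMRM list (minor improvement, no new data)

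*SAP*

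**What the plan says.** SAP Section 4 states the aim as "To explore the effect of starting dose (160 mg compared to 80 mg". Its endpoints there are "Onset of action and treatment response (ASAS, ASDAS, CRP, BASFI, BASDAI, spinal pain and SF-36 PCS". Protocol Table RHBX.1 has a shorter list, "Onset of action and treatment response (ASAS, ASDAS, CRP, BASFI". ASDAS is in both.

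SAP Section 6.1.2.1 turns this into analyses of two kinds:

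- Response rates by logistic regression, for "selected categorical variables (ASAS40/20, ASDAS<2.1, BASDAI50, ASDAS clinical important improvement, ASDAS major improvement".
- Mean change by MMRM: "LS mean change in selected continuous efficacy and health outcome measures (CRP, BASFI, BASDAI, spinal pain and SF-36 PCS) at Weeks 16 and 52".

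The MMRM includes starting dose, baseline value, visit and their interactions as needed. It is written once for comparisons within a regimen and once for both regimens together. The pooled logistic model is simpler: "Starting dose comparison combining ixekizumab Q2W and Q4W treatment regimens will be based on logistic regression model with only starting dose in the model". Differences with 95% confidence intervals are to be reported for both kinds.

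In Table RHBX.6.5 the ASDAS-change rows contain no starting-dose comparison. The binary ASDAS rows do, for example "Logistic regression analysis with NRI (for ASDAS <2.1 only".

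**The concern.** ASDAS is a continuous score. Against placebo, its change from baseline is a major secondary endpoint analysed by MMRM. For starting dose it is the only continuous measure named in the objective that is not compared on its full scale. BASDAI, a later addition to the objective, is given both a cut-off (BASDAI50) and mean change, so the SAP itself pairs the two forms elsewhere. No reason is given for treating ASDAS differently.

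What is at stake is the precision of one exploratory comparison. A threshold discards the distance of each patient from the cut, and the starting-dose logistic models carry no baseline covariate while the MMRM does. If the two starting doses differ modestly on ASDAS, the cut-off analyses are more likely to give an inconclusive interval than an analysis of the scores already collected.

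**Working it through.** **Inputs from the documents.** About 300 patients randomised 1:1:1, so about 100 per ixekizumab regimen. SAP Section 5.1 says "half the patients will be given a 160-mg starting dose and the other half will be given an 80-mg starting dose". That gives about 50 v 50 within a regimen and 100 v 100 pooled. No power, SD, response rate or effect is stated for any starting-dose comparison.

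**The nearest stated power.** ASAS40 at Week 16, 46% v 18%, 100 per group, two-sided Fisher's exact test at 0.05: full enumeration gives 98.8% against the stated 98% or so. The six Week 52 rows give 100.0, 99.9, 93.5, 100.0, 97.4 and 66.9% against 99, 99, 93, 99, 97 and 66%. The plan's own figures reproduce.

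**Worked example; every input is an assumption.** Baseline ASDAS 3.8 (SD 0.8), change -1.2 (SD 1.0) in the 80-mg group, correlation of baseline with change -0.4, two-sided 0.05, starting-dose difference δ of 0.3, 0.4 or 0.5 units.

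*Change score, adjusted for baseline.* Residual SD = 1.0 × √(1 − 0.16) = 0.917. Power = Φ(δ / (0.917 × √(2/n)) − 1.96). For δ = 0.3 and n = 50: 0.3 / 0.183 = 1.64, and Φ(1.64 − 1.96) gives 37%.

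*Cut at 2.1.* Mean follow-up score 3.8 − 1.2 = 2.6; SD = √(0.64 + 1.00 − 2 × 0.4 × 0.8 × 1.0) = 1.0. P(score < 2.1) = Φ(−0.5) = 0.309 in the 80-mg group and Φ(−0.2) = 0.421 with δ = 0.3. Log odds ratio 0.487, standard error 0.419, ratio 1.16, and Φ(1.16 − 1.96) gives 21%.

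| Power (%), δ = 0.3 / 0.4 / 0.5 | 50 v 50 | 100 v 100 |
|---|---|---|
| ASDAS change | 37 / 59 / 78 | 64 / 87 / 97 |
| ASDAS below 2.1 | 21 / 34 / 49 | 38 / 59 / 78 |
| Improvement of at least 1.1 | 22 / 34 / 48 | 38 / 59 / 77 |
| Improvement of at least 2.0 | 19 / 31 / 45 | 34 / 55 / 74 |

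From unrounded values, the loss within a regimen is about 16 to 29 points for the cut at 2.1, 16 to 30 for the 1.1 cut and 18 to 33 for the 2.0 cut. Pooled, over all three, it is about 19 to 32 points.

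Without reference to a significance threshold: at δ = 0.3, (1.16 / 1.64)² ≈ 0.50, so the cut carries about half the information of the baseline-adjusted change. Without baseline adjustment the change score has ratio 0.3 / 0.2 = 1.5, and (1.16 / 1.5)² ≈ 0.60. Part of the gap is therefore covariate adjustment; most is the cut.

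**Wider range.** No baseline adjustment, standardised effect d from 0.2 to 0.6, 80-mg-group response p0 from 10% to 50%, 160-mg-group response Φ(Φ⁻¹(p0) + d), normal-approximation power for means and for proportions:

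| Groups | d | p0 | Mean | Cut | Loss (points) |
|---|---|---|---|---|---|
| 50 v 50 | 0.2 | 50% | 16.9% | 12.1% | about 5 |
| 50 v 50 | 0.4 | 40% | 51.6% | 35.2% | 16.4 |
| 50 v 50 | 0.5 | 15% | 70.5% | 41.6% | 28.9 |
| 100 v 100 | 0.4 | 10% | 80.7% | 43.2% | 37.5 |

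Over the whole grid the loss is about 5 to 36 points within a regimen and 7 to 38 pooled. Every case tried shows a loss; only its size varies.

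**Limit of the calculation.** Logistic regression with NRI counts rescue and discontinuation as nonresponse, whereas the MMRM leaves out data after rescue. The figures compare the two scales on complete data. They do not compare two analyses of one estimand.

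**The tables beside Section 6.1.2.1.** Starting-dose rows exist in Table RHBX.6.5 for ASAS40, ASAS20, ASDAS below 2.1, the two ASDAS improvement endpoints, BASFI and CRP. Section 6.1.2.1 also plans BASDAI50, BASDAI change, spinal pain and SF-36 PCS by starting dose, and neither Table RHBX.6.5 nor Table RHBX.6.7 has such rows for them.

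**The case against.** The objective is worded as exploration, both lists are labelled as selections, and the protocol leaves the detail to the SAP. Three established ASDAS thresholds are compared, so the objective is met as worded, and ASAS too is handled only as response. Most of the content of ASDAS is also compared on a full scale: it is built from BASDAI questions 2, 3 and 6, patient global and CRP, and BASDAI and CRP are both in the MMRM list. Only patient global has no continuous starting-dose analysis. Nothing in the plan turns on p < 0.05 here, so power is an indirect measure of harm.

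All of this stands, and it is why the point is minor. It does not explain why the composite itself, named in the objective, lacks the analysis given to every other continuous measure beside it.

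Three stronger readings might be inferred, and the documents do not support them. The first is that ASDAS is missing from the starting-dose comparison: only its continuous form is. The second is that Table RHBX.6.5 singles ASDAS out: BASDAI change, BASDAI50 and spinal pain lack starting-dose rows there as well, as does SF-36 PCS in Table RHBX.6.7. The third is that a controlled endpoint is weakened: the major secondary status of ASDAS change belongs to ixekizumab against placebo, which this does not touch.

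**Conclusion.** The point holds as a small, avoidable loss of precision. ASDAS is named in the starting-dose objective, and its change from baseline is left out of the MMRM comparison that all the other continuous measures in that objective receive.

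A reader might take 16 to 29 points as a fixed cost. It is not: it belongs to one assumed set of means, SDs and correlation, for one cut-off within a regimen. About 5 to 38 points is the range over the wider inputs tried, and is itself not a bound. The direction is secure and the size is not. Because the comparison is exploratory, unpowered and outside the multiplicity scheme, no primary or major secondary conclusion is affected.

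**What to change.** In SAP Section 6.1.2.1, add ASDAS change from baseline to the continuous starting-dose measures, using the MMRM already specified there, within regimen and pooled. Keep the three cut-offs alongside it. If the omission was deliberate, state the reason instead.

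In the same edit, add starting-dose rows to Table RHBX.6.5 for ASDAS change, BASDAI change, BASDAI50 and spinal pain, and to Table RHBX.6.7 for SF-36 PCS, so that the tables match the text.

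The cost is one entry in a list, five table rows and one additional outcome through existing code. The ASDAS components are already collected at every scheduled visit from baseline to Week 52, so no new data are needed.
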